### 1. Abstract

An anonymous online survey measure parents and teachers' barriers and facilitators to influencing children's hand-hygiene and their own surface cleaning. A pilot survey was conducted with participants from the United Kingdom and India, and its results informed what survey items are used in the final survey. The final survey will be conducted with participants from Australia, China, India, Indonesia, Saudi Arabia, South Africa, and the United Kingdom. The data collected will be completely anonymous and there are no sensitive questions. Participants can withdraw simply by closing their browser windows. The primary and secondary analyses focus on the hand-hygiene items, and aim to examine their internal validity. Secondary analyses will look at the surveys external validity. Exploratory analysis will compare participants' responses across countries/regions, and individual differences. The survey results will inform a future school-based intervention and be written up for publication in an academic press acknowledging all collaborating organizations.

## 2. Introduction/Background

As urbanization increases so do socially-acquired infections and antibiotic use. This is a problem, because as antibiotic use become more prevalent so does antimicrobial resistance. The slow pace at which new antibiotics emerge on market necessitates preserving the effectiveness of existing antibiotics. The following attempts to do so are already in place: optimizing prescribing, educating the public, and increasing hygiene. The present study focuses on the last effort: increasing hygiene.

The World Health Organization describes hygiene as “practices that help to maintain health and prevent the spread of diseases.” These practices include behaviors to disinfect one’s body and surrounding environment. Improving community health may require a multifaceted intervention that targets hand-hygiene and environment-disinfecting to stop reinfection cycles. Interestingly, the cleanliness of the environment itself may play a role in people’s hygiene behaviors. For example clean scents encouraged people to clean their table scraps  and settings with no litter decrease people’s tendency to litter. School have proven an effective delivery platform to increase community health. Within these interventions children are often believed to be “agents of change” who carry lessons from school to the broader community.

To inform the development of future school-based interventions, the current study seeks to develop a survey to identify the most common reasons adults are not already positively influencing school children’s hand-hygiene. Identifying the most common reasons is important, because interventions that target uncommon or misinformed reasons are unlikely to yield practically significant improvements. The list of possible reasons includes the behavioral determinates described by the Theoretical Domains Framework (TDF;). Specifically, the present study aims to assess adults’ tendencies to positively influence children’s hand-hygiene with regards to their: Knowledge, Skills, Memory, attention and decision processes, Behavioral regulation, Social/professional role and identity, Beliefs about capabilities, Beliefs about consequences (inclusive of Optimism and Reinforcement), Intentions (inclusive of Goals), Emotion, Environmental context and resources, and Social influences.

In the current study, a survey will be designed to measure each TDF domain. In addition, because the cleanliness of the surrounding environment also influence cleaning behaviors, a sub-component of the survey will assess adults’ tendencies to disinfect surface areas where children play and learn. The survey will be rolled-out across several countries/regions. The primary and secondary analyses will to validate the internal and external features of the hand-hygiene survey component. Secondary analyses will look at the surveys external validity and internal validity across each country/region. Exploratory analysis will be used to compare participants’ responses across countries/regions, and individual differences. The results of this survey will be used to inform a future school-based intervention.

### 3. Aims of Study

The current study aims to conduct and examine the validity of a survey that survey aims to assess the behavioral determinates that affect adults' tendency to positively influence children's hand-hygiene. We also look at determinants that affect surface cleaning.

### 4. Objectives

Objective 1. Roll-out a final draft surveys in the different countries/regions.

Objective 2. Conduct a confirmatory factor analyses on the hand-hygiene component of the survey.

Objective 3. Conduct regression analyses to determine whether participants' responses on the hand-hygiene component of the survey predict their self-reported confidence.

Objective 4. Compare participants' responses across each domain, country, and individual difference.

### 5. Hypothesis

#### 5a. Primary Hypothesis

The primary hypothesis relates to Objective 2.

The TDF determinates will describe the hand-hygiene data well.

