Appendix A presents a list of the domains, their definitions, and survey items about hand-hygiene influencing.

The hand hygiene items will appear in a random order.

In the final survey, we aim to assess each of 11 behavioral determinates using at least 3 items that can be responded to with a 5-point Likert scales, where 1=strongly disagree and 5=strongly agree. Some items will be reverse scored to mitigate acquiescence bias.

- **Survey Section 4: Surface disinfecting.**

Appendix A presents a list of the domains, their definitions and survey items about hand-hygiene influencing.

The surface cleaning items will appear in a random order.

In the final survey, we aim to assess each of 11 behavioral determinates using at least 1 item that can be responded to with a 5-point Likert scales, where 1=strongly disagree and 5=strongly agree. Some items will be reverse scored to mitigate acquiescence bias.

- **Survey Section 5: Self-reported confidence (3 items).**

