## 12b. Statistical methods

As a reminder, the sample-size is designed to support a factor analysis for the hand-hygiene component of the project. The surface cleaning component of the project will only be analyzed using descriptive and exploratory methods.

Software: The data will be analysed using the most recently available copies of SPSS and SPSS: AMOS.

Descriptive: Frequencies, percentages, averages and confidence intervals will be used to describe the participants' responses and demographics.

Internal Consistency: Cronbach's alphas will be calculated. Items will be removed as necessary to achieve an alpha coefficient of 0.70 or above within each domain; those coefficients as low as 0.65 will be tolerated if necessary to retain the planned model.

[figure not shown]
Confirmatory Factor Analyses (CFA) - Objective 4: CFA will be performed to test whether the data from the items fit within the pre-determined components.

The first models (the primary analyses) will be conducted with the data from all the countries and then additional models (the secondary analyses) will be conducted with each country.

The models will be specified in AMOS and tested for goodness of fit using three indices: (a) absolute fit (based on a Chi-squared to degrees of freedom ratio, less than 2; ), (b) parsimony (based on Root Mean Square Error of Approximation (RMSEA) of close to or less than 0.06), and comparative fit (based on an index 'close to' 0.95; ). The models may be revised until the desired measures of fit are obtained.

Figure will be created to describe the final models' structure. An example of a figure like this with only 2 determinates appears below (Figure 2):

Figure 2. Example of a CFA model

Regression analyses - Objective 5: Multiple regression analysis will be conducted, overall and for each country. The predictors will be participants' average responses to each behavioural determinate, and the outcome will be participants' average responses to the confidence items. An alpha value of 0.05 will be used to assess each predictors' contribution to the overall model.

Exploratory Analyses - Objective 6: The participants' individual differences will be compared using graphical analyses (bar charts with error bars) and statistical tests (e.g., ANOVAs). Their content is not further specified within this protocol.

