Appendix A. Survey items (finalized 09-Apr-2020)

Domain	Question Number	Handwashing Surface Disinfection	Parents	Teachers
Knowledge An awareness of the existence of something	1	H	I know that my children should wash their hands with soap and water for at least 20 seconds.	I know that my pupils should wash their hands with soap and water for at least 20 seconds.
	2	H	(RS) I do not know when my children should wash their hands with soap and water.	(RS) I do not know when my pupils should wash their hands with soap and water.
	3	H	(RS) I know that when my children's hands look clean, they are germ free.	(RS) I know that when my pupils hands look clean, they are germ free.
	4	SD	(RS) I know that when surfaces look clean, there are no germs.	(RS) I know that when surfaces look clean, there are no germs.
	5	SD	I know which surfaces I should disinfect in the home.	I know which surfaces I should disinfect in the classroom
Skills An ability or proficiency acquired through practice	6	H	I am able to teach my children to wash their hands.	I am able to teach my pupils to wash their hands.
	7	H	I am able to help my children develop good handwashing habits.	I am able to help my pupils develop good handwashing habits.
	8	H	(RS) I am not able to teach my children to wash their hands.	(RS) I am not able to teach my pupils to wash their hands.
	9	SD	I have the ability to disinfect surfaces in the home.	I have the ability to disinfect surfaces in the classroom
	10	SD	(RS) I do not have the ability to disinfect some of the surfaces in the home.	(RS) I do not have the ability to disinfect some of the surfaces in the classroom
Memory, attention and decision processes The ability to retain information, focus selectively on aspects of the environment and choose between two or more alternatives	11	H	I remind my children to wash their hands before eating.	I remind my pupils to wash their hands before eating.
	12	H	(RS) I forget to remind my children to wash their hands.	(RS) I forget to remind my pupils to wash their hands.
	13	H	(RS) There are many distractions that cause me to forget to remind my children to wash their hands.	(RS) There are many distractions that cause me to forget to remind my pupils to wash their hands.
	14	SD	I remember to disinfect the surface areas in my home every day.	I remember to disinfect the surface areas in the classroom every day.

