	27	H	(RS) I do not believe I can control whether my children wash their hands.	(RS) I do not believe I can control whether my pupils wash their hands.
	28	H	I believe that I can tell my children to wash their hands with soap and water.	I believe that I can tell my pupils to wash their hands with soap and water.
	29	SD	I believe that I am capable of disinfecting surfaces in my home.	I believe that I am capable of disinfecting surfaces in the classroom .
	30	SD	(RS) I believe that there is little I can do to disinfect surfaces in my home.	(RS) I believe that there is little I can do to disinfect surfaces in the classroom
Beliefs about consequences/ Optimism / Reinforcement (Belief) Acceptance of the truth, reality, or validity about outcomes of a behaviour in a given situation (Optimism) The confidence that things will happen for the best or that desired goals will be attained (Reinforcement) Increasing the probability of a response by arranging a dependent relationship, or contingency, between the response and a given stimulus	31	H	I believe that telling my children to wash their hands with soap and water will protect them from falling ill.	I believe that telling my pupils to wash their hands with soap and water will protect them from falling ill.
	32	H	(RS) I believe that children's handwashing habits have little effect on whether they get ill.	(RS) I believe that pupil's handwashing habits have little effect on whether they get ill.
	33	H	(RS) I believe that teaching my children to wash their hands is not worthwhile.	(RS) I believe that teaching my pupils to wash their hands is not worthwhile.
	34	SD	I believe that if I disinfect my home, my children will all fall ill less often.	I believe that if I disinfect the classroom my pupils will all fall ill less often.
	35	SD	(RS) I believe that disinfecting my home has no effect on how often my children get ill.	(RS) I believe that disinfecting my classroom has no effect on how often my pupils get ill.
	36	H	I intend to keep reminding my children to wash their hands before eating.	I intend to keep reminding my pupils to wash their hands before eating.

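### Good fit of the 11-factor CFA does not show that the 11 TDF domains are distinct: if the factors may correlate, lack of distinctness cannot by itself make the fit criteria fail

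*Combined protocol and SAP*

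**What the plan says.** Section 5a states the primary hypothesis: "The TDF determinates will describe the hand-hygiene data well". Section 11 gives the structure: "we aim to assess each of 11 behavioral determinates using at least 3 items that can be responded to with a 5-point Likert scales". Appendix A lists three hand-hygiene items per domain.

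Under section 12b, "CFA will be performed to test whether the data from the items fit within the pre-determined components". Fit is judged by three indices. The first is "absolute fit (based on a Chi-squared to degrees of freedom ratio, less than 2"; the second is an RMSEA near or below 0.06; the third is an unnamed comparative index near 0.95. Section 12b also says that "The first models (the primary analyses) will be conducted with the data from all the countries". The secondary models repeat the exercise country by country and name no different factor structure. Models may be respecified until the fit targets are met. Cronbach's alpha is calculated within each domain.

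The plan names no one-factor, reduced, second-order or bifactor alternative, no criterion for comparing models, and no limit on factor correlations. It does not say whether the factors may correlate; the example diagram (Figure 2) is not available in the text reviewed.

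**The concern.** The purpose in section 2 is diagnostic: "the current study seeks to develop a survey to identify the most common reasons adults are not already positively influencing" children's hand hygiene, so that an intervention can target the right ones. That requires the domains to be separable. The criteria in 12b ask whether 11 factors reproduce the item covariances, not whether fewer would do equally well. Alpha does not fill the gap, because it measures consistency within a domain. Nor does the comparative index: read as CFI, its baseline is the model of unrelated items, not a simpler factor model.

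At stake are the later analyses: domain averages, comparisons by country, and a regression in which each domain average is tested at 0.05. If domains are not separable, these results are labelled by domain without a basis for the labels.

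The item wording gives some reason to look. Item 11 (Memory) reads "I remind my children to wash their hands before eating" and item 36 (Intentions) reads "I intend to keep reminding my children to wash their hands before eating". Item 6 (Skills) and item 28 (Beliefs about capabilities) both ask about being able to instruct the child. This is a reason to check, not evidence that the domains coincide.

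**Working it through.** **Inputs from the documents.** There are 11 domains × 3 items = 33 items (section 11, Appendix A). Table 2 gives India 375 + 375 + 75 = 825 and each of six other countries 225 + 225 + 75 = 525, so the pooled N is 825 + 6 × 525 = 3,975.

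**Assumptions.** Factors are freely correlated, with no cross-loadings. Loadings are 0.70 (0.75 for skewed items). The comparative index is CFI. A pass means chi-square/df < 2, RMSEA ≤ 0.06 and CFI ≥ 0.95.

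**1. The plan's own sample-size rule.** Parameters: 33 loadings + 33 residual variances + 55 factor correlations = 121. The rule of 10 to 20 participants per parameter (section 12a) needs 1,210 to 2,420. The pooled sample gives 3,975/121 = 32.9 per parameter, so the rule is met for the primary model under this count. Country models have 825/121 = 6.8 or 525/121 = 4.3, a separate matter.

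**2. Nesting.** The model is Σ = ΛΦΛ′ + Ψ, with 33 × 34/2 = 561 moments and df = 561 − 121 = 440. Setting all 55 off-diagonal elements of Φ to 1 gives the one-factor model (df = 495). The 11-factor chi-square can therefore never exceed that of a model with domains merged. If the merged model is true, so is the 11-factor model, and its expected chi-square/df is about 1.

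**3. Simulation from one common factor, fitting 11 factors by maximum likelihood.** RMSEA = √[max(T − df, 0)/(df(N − 1))]; CFI = 1 − max(T − df, 0)/max(T₀ − df₀, T − df), where T₀ and df₀ belong to the model of unrelated items.

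| Items | N | Runs | χ²/df | RMSEA | CFI | All three passed |
|---|---|---|---|---|---|---|
| Continuous | 3,975 | 60 | 1.01 | 0.002 | 0.9998 | 100% |
| Continuous | 825 | 60 | 1.02 | 0.005 | 0.999 | 100% |
| Continuous | 525 | 60 | 1.03 | 0.007 | 0.998 | 100% |
| 5-point, symmetric | 3,975 | 40 | 1.02 | 0.002 | 0.9997 | 100% |
| 5-point, skewed | 3,975 | 40 | 1.31 | 0.009 | 0.998 | 100% |
| 5-point, skewed | 525 | 40 | 1.33 | 0.025 | 0.985 | 100% |

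In every run the estimated factor correlation matrix was not positive definite, and about half of the correlations exceeded 1. The loading is in line with the plan's alpha target: with r = 0.7² = 0.49, alpha for three items is 3r/(1 + 2r) = 1.47/1.98 = 0.74.

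**4. Would a comparator tell the difference?** BIC prefers 11 factors if T₁ − T₁₁ exceeds 55 ln N, which is 455.8 at N = 3,975 and 344.5 at N = 525. From the mean chi-square/df values:

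| Truth | N | T₁ − T₁₁ | BIC prefers |
|---|---|---|---|
| One factor, continuous | 3,975 | 1.012 × 495 − 1.012 × 440 = 55.7 | one factor |
| One factor, skewed 5-point | 525 | 1.327 × 495 − 1.330 × 440 = 71.7 | one factor |
| 11 factors, correlation 0.9 | 3,975 | 2.831 × 495 − 1.011 × 440 = 956.5 | 11 factors |
| 11 factors, correlation 0.9 | 525 | 1.268 × 495 − 1.020 × 440 = 178.9 | one factor |
| 11 factors, correlation 0.7 | 525 | 2.545 × 495 − 1.022 × 440 = 810.1 | 11 factors |

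The plain chi-square difference test (55 df) detected 11 factors in all runs at correlations 0.7 and 0.9. On one-factor data it favoured 11 factors in 3% to 5% of runs with continuous items, but in 35% (N = 3,975) and 53% (N = 525) with skewed 5-point items.

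**5. Effect on the regression.** With one true factor, N = 3,975 and an assumed correlation of 0.3, 0.5 or 0.7 between factor and outcome, roughly 2, 5 or 10 of the 11 domain averages come out significant. As the domains are equivalent by construction, which ones do so is chance.

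**The case against.** **Correlated factors are assumed.** This stands. With uncorrelated factors, one-factor data fail clearly (loading 0.70: RMSEA about 0.15, CFI about 0.39). The text does not say which is meant, so the point is conditional.

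**The passing solutions are improper.** This also stands. An analyst would see correlations above 1 and might stop. The plan, however, makes neither admissibility nor the size of correlations a criterion.

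**Real data are not a pure single factor.** A reader might infer that any one-factor data would pass the primary analysis, or that the analysis cannot fail. Neither follows. Of the 33 items, 17 are reverse-scored. Adding a shared reverse-wording effect (assumed loading 0.2, 0.3 or 0.4) to one-factor data gives expected chi-square/df of 2.3, 5.8 or 12.1 at N = 3,975, all above 2. At that N the limit of 2 corresponds to RMSEA below √(1/3,974) = 0.016. RMSEA and CFI still pass or come close, and at N = 525 the 0.2 and 0.3 cases pass the ratio. But such a failure reflects wording, and 12b then permits revision until fit is reached.

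**Items 11 and 36 overlap as single items.** A model without cross-loadings does penalise that. With domain correlations of 0.5 to 0.7, an assumed residual correlation of 0.5 between them gives chi-square/df of 2.5 to 2.7 at N = 3,975; at 0.3 it is about 1.5. This pair therefore does not illustrate domains that merge.

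**The hypothesis says only that the determinants describe the data.** That is a fair reading of 5a. It does not rescue the later analyses, which treat the determinants as 11 separate quantities.

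**Conclusion.** The concern holds in conditional form. If the 11 factors are free to correlate, lack of distinctness cannot by itself make the three criteria fail, and good fit alone does not support 11 separate determinants. Simulated pure one-factor data passed in 100% of runs in every scenario, with improper factor correlations that the plan would not count as failure. This rests on the assumed loadings, no cross-loadings, CFI as the comparative index and strict readings of the two limits worded as approximate.

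A reader might also infer that the real domains are indistinguishable. The documents contain no data on factor correlations, so that is not supported. The gap is in what the test can show. It should be closed, but it calls for no change to the survey or the sample.

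**What to change.** In section 12b:

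- State that the factors are freely correlated.
- Fit a one-factor model beside the 11-factor model, on the same final item set. If wanted, add one reduced model whose mergers are fixed before the data are seen.
- Compare the models by BIC and change in CFI, with the CFI threshold fixed in advance, and not by a plain maximum-likelihood chi-square difference alone.
- Require an admissible solution.
- Report the 55 factor correlations with 95% confidence intervals, by bootstrap or another method suited to 5-point items.
- Claim support for 11 distinct determinants only if the 11-factor model is preferred and the correlations fall below a limit set in advance. Otherwise, report which domains cannot be separated.

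The limit and any mergers are for the study team to choose. Two cautions apply. At N = 525, BIC would favour one factor even at true correlations of 0.9, so country results need the correlations beside them. At true correlations of 0.95 a one-factor model reached CFI 0.996 in simulation, which leaves at most 0.004 for change in CFI to detect.

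The cost is a few extra models on data already being collected, some interval estimation, a paragraph of text, and a primary claim that is harder to meet.

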#### 5b. Secondary Analysis

The first secondary hypothesis relates to Objective 2.

The TDF determinates will also describe the hand-hygiene data well across each country/region.

The second secondary hypotheses relates to Objective 3.

The TDF determinates will predict participants' hand-hygiene related self-reported confidence in influencing children's hand hygiene well as a whole and across each country/region.

## 5c. Exploratory Analyses

The exploratory analyses relate to Objective 4.

Participants' hand-hygiene responses across individual difference will be explored using averages and confidence intervals.

Participants' surface disinfecting responses will be assessed as a whole and then compared across countries and individual differences using averages and confidence intervals.

## 6. Study Design

An anonymous online survey will be used, because it can be rolled-out quickly to collect data from a large numbers of participants in different places. No IP address or other geolocation information will be collected.

We will roll-out the final survey to a large adult participants in Australia, China, India, Indonesia, Saudi Arabia, South Africa, and the United Kingdom.

